5.1 Study Design

The laboratory study will include several experimental conditions, being a combination of supported seating or unsupported standing by the exoskeleton, and three different working heights. These seven combinations will be offered to the subjects in a balanced, randomized cross-over design (Latin Square Williams Design; Williams 1949). In each of these seven conditions, three manual materials handling tasks will be simulated in a fixed order but in three different frontal working distances. Because of the three working distances, we will include a multiple of the 14 orders resulting from the Williams Design, striving for a population of 42 subjects.

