7.6 Subjective Assessment

Participants will rate their overall subjective feeling of discomfort (RPD) on a 11-point numerical rating scale (McCaffery & Beebe 1989; Figure 6; Attachment 3). When participants experience a feeling of discomfort > 0, we ask them to define the body region (Kuorinka et al. 1987) which is causing this sensation.

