7.7 Participant Evaluation

When the participants have finished the experiment, we will provide them with a short questionnaire to report their opinion about using the exoskeleton for the various experimental conditions. This will provide us information about the acceptance of the worker regarding the use of the 'Chairless Chair'. The questionnaire will include items on feasibility, comfort, and usability (Attachment 6).

8 Statistical Analysis

When all data are collected, we will have a number of dependent variables as listed in Table 3. Each of these parameters will provide a(n) (average) value per condition, resulting in four values. For the continuous measurements, i.e. posturography, muscle strain, and work performance, we will average the values over each of the seven conditions. For the discontinuous measurements, i.e. subjective discomfort ratings, we will calculate the difference value of the pre- and post-condition measurements. Participant evaluations will not be tested but only discussed narrative.

Table 3. Summary of the model components that will be included in the statistical analyses.

Model component	Method / Name	Parameter
Dependent variable	Posturography	Center of Pressure (COP) Joint angles
	Muscle strain	Amplitude (ARV) Median power frequency (MdPF)
	Work performance	Error rate Timing error
	Subjective assessment	Rating of perceived discomfort (Borg RPE)
Within-subject factor	Working postures	Without, with (high), with (low) exoskeleton
	Working height	High, medium, low
	Working distance	Optimal, too far I, too far II
Between-subject factor	Group	Body height (S/M/L)

The current study has a repeated measures design including three within-subject factors (*exoskeleton*, *working height*, and *working distance*). If we have enough participants, we could also include a between-subject factor (*group*, based on body height), or another post-hoc identified discriminator. We will use a linear mixed effects model to perform the statistical analyses of all dependent variables (Table 3) using SPSS (IBM SPSS Statistics 23.0). This model allows observations to be not independent, because it adds a *random effect* for subject, i.e. modeled by assuming different *random intercepts* for each subject. This model also allows including both repeated measures, i.e. different conditions (within-subject factor: *working height*, *working posture*, *working distance*), and comparing independent groups of participants (between-subject factor: *group*).

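### Section 8 leaves the number of values per man unresolved and names only a subject intercept and no period term, so standard errors can be wrong in either direction

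*Combined protocol and SAP*

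**What the plan says.** All of this is in section 8 unless noted.

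- Number of values. Each parameter yields a "value per condition, resulting in four values". For posturography, muscle strain and work performance, "we will average the values over each of the seven conditions". The design is then described differently: "The current study has a repeated measures design including three within-subject factors", the third being working distance. Section 5.1 has the tasks in each condition "simulated in a fixed order but in three different frontal working distances", so distance varies inside a condition.
- Discomfort. Section 7.6 asks for one overall rating, and for its analysis "we will calculate the difference value of the pre- and post-condition measurements". That is one value per condition.
- Model. "We will use a linear mixed effects model to perform the statistical analyses of all dependent variables". Dependence within a man enters through a subject effect, "modeled by assuming different *random intercepts* for each subject". Neither Table 3 nor the model text contains period, order or sequence.
- Setting. Section 6.1 runs all seven conditions in one visit, each about 20 minutes with 3-minute breaks. Section 9 lists muscle fatigue as the session goes on among the possible side effects. Section 5.5 calls the study a pilot that is to supply the basis for sizing follow-up projects.

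**The concern.** The data set is not defined. With seven means per man, distance cannot be estimated. With 21 values it can, but three values from one condition are then treated as no more alike than values from different conditions. Discomfort cannot carry a distance factor on either reading.

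A subject intercept assumes that all values from one man are equally correlated. With 21 values this fails if conditions vary within men or if men respond differently to distance. With seven means it fails if men respond differently to posture or to height. Without a period term, drift over the session goes into the residual.

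At stake are the tests of posture and height, for which the study is built, and the pilot's purpose: the model as written does not estimate how much men differ in their response to posture, height or distance, and a follow-up sample size needs those variances.

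**Working it through.** **Inputs.** From the documents: seven conditions, three distances, the 14 orders of Figure 1B, and 42 men. The 42 reproduces as 14 orders × 3 distance orders. There is no power calculation to reproduce, and no alpha, variance or drift is given.

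Assumed: 5% level, no true effect, main-effects model, single-value residual variance 1 (so 1/3 for a mean of three), and three cyclic distance orders because Attachment 8 is not available. Cell E is taken as high seating at low height, as Figure 1A ticks it; the printed key gives E the same label as G.

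**1. Values per man.** Seven means give 42 × 7 = 294 values; a distance factor needs 42 × 21 = 882. Four cannot be derived from seven conditions.

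**2. Twenty-one values, subject-by-condition variance v.** Residual degrees of freedom are 6 × 42 − 4 = 248 between conditions and 14 × 42 − 2 = 586 within them, total 834. The intercept-only model uses the pooled mean square [248(1 + 3v) + 586]/834. The correct error is 1 + 3v for posture and height and 1 for distance. For a 2-df test the large-sample false-positive rate is exp(−2.996 × pooled/correct).

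| v | pooled | posture, height | distance |
|---|---|---|---|
| 0.1 | 1.089 | 8.1% | 3.8% |
| 0.25 | 1.223 | 12.3% | 2.6% |
| 0.5 | 1.446 | 17.7% | 1.3% |

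With subject-by-distance variance 0.25 instead, simulation gives about 27% for distance and 3% for posture and height.

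**3. Seven means, subject-by-posture variance p.** Each posture covers 2, 3 and 2 cells, so p enters each man's within-man sum of squares with factor 7 − (4 + 9 + 4)/7 = 4.571. The expected residual mean square is {42(2 + 4.571p) − (4/3 + 4.571p)}/248. Low seating versus standing, and low versus high height, each have a per-man variance of 4/3 times the residual.

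- p = 0, no drift: the model is correct, and the rate is about 5%.
- p = 0.11, a share of 0.11/(0.11 + 0.333) = 25%: mean square 0.4165. Simulated rates are about 10% for posture and 3% for height.
- p = 0.5, a share of 60% and an extreme case: mean square (180 − 3.619)/248 = 0.711. The model's standard error is √(0.711 × 1.333/42) = 0.150. The true one is √[(2 × 0.5 + 0.444)/42] = 0.185 for low seating versus standing (ratio 0.81) and √(0.444/42) = 0.103 for low versus high height (ratio 1.46). Simulated rates are about 20% and 0.3%.
- Posture and height variances both 0.11, or both 0.5: about 7% or 9% for each factor. The standard error ratio is about 1.0 for the extreme contrasts and 0.94 or 0.88 for adjacent levels.

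**4. Period.** In Figure 1B each condition occurs twice in every period and each of the 42 ordered pairs occurs twice. In complete data, drift therefore cancels from the estimates and stays in the residual. A linear drift of D single-value SDs over the seven periods adds 28(D/6)² per man. On seven means the standard error is multiplied by √{[1/3 + 42 × 28(D/6)²/248]/(1/3)}, which is 1.05, 1.18 and 1.61 for D = 0.5, 1 and 2. On 21 values, D = 2 gives √(1 + 3 × 42 × 3.11/834) = 1.21. Drift can also hide the error in step 3: with p = 0.5 and D = 2 the posture rate is about 6% without a period term and 20% with one.

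**5. Follow-up size, extreme contrasts, seven means.** With p = 0.5 and no subject-by-height variance, a same-design follow-up needs (0.1854/0.1503)² = 1.52 times the men for posture and (0.1029/0.1503)² = 0.47 times for height, relative to what the stated model suggests. With both variances at 0.5 the multiplier is about 1 for these contrasts and 1/0.88² = 1.29 for adjacent levels.

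**The case against.** This is a pilot with no stated alpha or hypothesis, and every error rate above rests on variances that the documents do not give. On seven means the intercept-only model is correct under equal correlation without drift. The large seven-mean figures need a subject-by-posture variance bigger than the residual. When men differ about equally in their response to posture and to height, most of the error cancels for the extreme contrasts. Section 8 also says that the model can accommodate repeated measures, which may hint at a residual covariance structure, and it does not exclude interactions. A richer random part may be hard to fit with the 21 men that section 5.5 accepts.

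Most of this stands as a limit on size: the percentages are illustrations for a main-effects model. It does not remove the point. The conflict over values per man and the discomfort problem need no assumed variances, and the hint about repeated measures names no covariance structure.

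Three stronger readings are tempting. A reader might infer that the posture effect will be overstated; the documents do not support this, because the net direction depends on unknown variances and drift. A reader might infer that the missing period term biases the comparisons; the printed orders are balanced, so in complete data it does not. A reader might take 1.52 and 0.47 as expected corrections to a follow-up; both belong to the one-sided extreme case in which men differ in their response to posture and not to height.

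**Conclusion.** The point holds as a gap in specification. Section 8 contradicts itself on values per man, gives discomfort a factor it cannot carry, and names neither a period term nor any within-man dependence beyond a subject intercept. Confidence in these statements is high.

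The consequence is that standard errors can be wrong in either direction. In the illustrations, false-positive rates for posture and height run from about 8 to 18% on 21 values when conditions vary within men. On seven means they run from nominal to about 10% for the affected factor at a 25% share, with 20% only in the extreme case; a factor to which men respond alike is tested too conservatively. Omitted drift of 0.5, 1 or 2 SDs makes seven-mean standard errors about 5, 18 or 61% too large. For the extreme contrasts, the follow-up sample size could be unaffected or off by up to the one-sided multipliers in step 5. All sizes assume 42 men with complete data, a 5% level and a main-effects model. This should be fixed before analysis.

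**What to change.** In section 8:

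- State for each outcome whether 7 or 21 values per man are analysed, and delete the statement of four values.
- Drop distance from the discomfort model and from any outcome analysed as seven means.
- In all models, add fixed period (1–7) and, beside the subject intercept, random subject-by-posture and random subject-by-height.
- Where 21 values are analysed, also add fixed distance time-slot (1–3), random subject-by-condition and random subject-by-distance.
- Use Satterthwaite degrees of freedom.
- Fix in advance the order in which the model is simplified if the fit fails, rather than choosing it from the estimates. A variance estimated at zero is fixed at zero; period, and with 21 values subject-by-condition, are always kept.
- Report the variance components for the follow-up sample size.

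Period should not be added alone: it removes the masking and leaves the error from the missing random terms.

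In simulation with 42 men this model held false-positive rates of 3.9–5.5% (posture) and 4.1–6.3% (height) on seven values, and 3.9–6.0%, 3.0–5.6% and 3.8–4.9% (posture, height, distance) on 21 values. All those fits converged, so the simplification rule was not exercised, and 21 men were not tested.

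The cost is a few lines of text and SPSS syntax, with no new data. The fit is more complex and may be less stable at 21 men. Some standard errors grow and others shrink: in the p = 0.5 example, posture goes from 0.150 to 0.185 and height from 0.150 to about 0.10.

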5.1.1 Independent variables (within-subject factors)

At first, experimental conditions are designed by a combination of working position and working height. We will investigate three different working positions [P]: (1) unsupported standing [US], (2) supported high seating [HS], and (3) supported low seating [LS]. We will investigate three working heights [WH]: high [H], medium [M], and low [L]. The combination of these two independent variables is displayed in Figure 1A. The randomized design for assigning conditions to subjects will be based on an orthogonal Latin Square Design (Figure 1B). A third independent variable considered is working distance, i.e. the distance of the task set-up from the front of the subject: (1) optimal, (2) far, (3) very far; the order of these three working distances will also be varied by assigning them balanced to the subjects. For the order of the three working distances, the outcome of a special type of Latin Square Design, the Williams Design suggests three different orders (for the complete experimental design, see Attachment 8).

A	WH _H	WH _M	WH _L	B	1	2	3	4	5	6	7	8	9	10	11	12	13	14
P_{SS}	V	V	X	1	A	B	C	D	E	F	G	D	E	F	G	A	B	C
P_{HS}	V	V	V	2	G	A	B	C	D	E	F	E	F	G	A	B	C	D
P_{LS}	X	V	V	3	B	C	D	E	F	G	A	C	D	E	F	G	A	B
				4	F	G	A	B	C	D	E	F	G	A	B	C	D	E
				5	C	D	E	F	G	A	B	B	C	D	E	F	G	A
				6	E	F	G	A	B	C	D	G	A	B	C	D	E	F
				7	D	E	F	G	A	B	C	A	B	C	D	E	F	G

A $P_{SS}WH_H$
B $P_{SS}WH_M$
C $P_{HS}WH_H$
D $P_{HS}WH_M$
E $P_{LS}WH_L$
F $P_{LS}WH_M$
G $P_{LS}WH_L$

Figure 1. A. Incomplete Block Design (Williams Design) based on position (P) and working height (WH), resulting in 7 different experimental conditions; B. Latin Square Design for 14 subject, which will be preferably elongated to a replicate of 14 subjects.

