6.1 Experimental Procedure

Before the experiment starts, participants will visit the lab for familiarization with the 'Chairless Chair' and familiarization with the three manual materials handling tasks. They will perform the simulated assembly tasks for about 30 to 45 minutes, of which 15 to 30 minutes while wearing the exoskeleton (3.8 kg) in the different positions. During this first visit, the subjects will also complete the form with general information (Attachment 1), the form with in-/exclusion criteria (Attachment 2) and will be explained in a standardized way about how to report and judge subjective feelings of discomfort (Attachment 3). After familiarization, participants will visit the laboratory a second time during which they will perform the seven experimental conditions (exoskeleton [3], working height [3]) in a preset balanced randomized order (using a Williams Design). Before starting with the true experiment, participants will first be equipped with the measurement devices. After the preparations, participants will perform each experimental condition for ~ 20 min followed by 3-min rest breaks. During the rest break the participant will first walk around and then sit down with wearing the exoskeleton.

After finishing the experimental conditions, subjects will perform 11 trials on the force plate. Two trials will be performed while the subject is wearing the exoskeleton and is standing (1) with only his feet on the force platform while the feet of the 'Chairless Chair' are off the force platform. The trials will be recorded while in low seating and in high seating when wearing the exoskeleton and performing one work cycle in optimal height. These trials should provide insight into the body weight distribution over the own feet and the exoskeleton. Nine other trials will be performed to provide insight into the center of pressure's behavior when performing tasks in different lateral workspaces. The nine trials will include three different positions (unsupported standing, supported high seating, supported low seating) and three different frontal-lateral workspaces (narrow in a range of 120° ,

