9 Risk for the Participant

The experiment has no threatening risks for the participant. However, there can be some side-effects of study-related procedures about which we will inform the participant, including:

- Skin irritation or reddening due to skin preparation and of the attachment of the adhesive electrodes; in rare cases, participants may experience allergic reactions;
- Tingling or tension sensations in the area of the adhesive electrodes due to cable pull;
- Sensations of tension or muscle fatigue along the duration of the experiment;
- Possible sensations of dizziness, loss of blood pressure, and a very low risk of impotence due to the semi-standing for a total of 70 minutes.

10 Data Protection

The participants as well as their personal and recorded data will be numerically pseudonymized by assigning a randomly generated, five-digit identification number to the examined participant.

Relating analyzed outcome data to the natural person is only possible by inspection of the decoding list. This list, together with the informed consents of all volunteering participants, will be stored separately from the measured data in the storage of the Institute of Occupational and Social Medicine and Health Services Research. All these participant data will be stored for a period of ten years after publication of the results. The destruction of the data in paper form is carried out by means of the disposal boxes for data protection at the University Hospital, and the destruction of the data in electronic form is carried out by means of transferring the data off the memory cards of the devices.

The measurements as part of this proposal are all recorded on portable computers that are accessible by means of a password only and cannot be accessed by any network. The pseudonymized data are processed within the University Hospital (UKT) network, of which the time of the measurement collection is removed from the operating software whenever possible. The measuring devices are configured identically for all measurements to exclude a possible association between the measurement configuration and the participants. After completing the data analysis, the data of the participants are stored together with the photo documentation on Blu-ray discs.

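### Section 9's 70 minutes of semi-standing is neither defined nor derived, and it does not match the roughly 100 minutes of supported work scheduled in Section 6.1 and Figure 1

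*Combined protocol and SAP*

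**What the plan says.** Section 9 (Risk for the Participant) lists side-effects of study procedures that participants are to be informed about. The last item names dizziness, loss of blood pressure and a "very low risk of impotence due to the semi-standing for a total of 70 minutes".

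Section 6.1 sets the schedule. After familiarization, "participants will visit the laboratory a second time during which they will perform the seven experimental conditions", and they "perform each experimental condition for ~ 20 min followed by 3-min rest breaks". For the breaks it says: "During the rest break the participant will first walk around and then sit down with wearing the exoskeleton". Eleven force-plate trials follow. At the earlier familiarization visit participants work for 30 to 45 minutes, "of which 15 to 30 minutes while wearing the exoskeleton (3.8 kg) in the different positions".

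Section 5.1.1 defines three positions: unsupported standing, supported high seating and supported low seating. Figure 1 crosses these with three working heights, "resulting in 7 different experimental conditions".

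The word *semi-standing* appears only in Section 9. It is not one of the three position names.

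**The concern.** Section 9 ties named side-effects to a duration, so the duration is part of the risk description. A reader should be able to recover it from the schedule by counting conditions and multiplying by their length. That attempt fails. On the most direct reading, in which semi-standing is work supported by the device, the schedule gives a clearly longer exposure than the one stated.

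At stake is the accuracy of a safety-related statement, and whether the ethics committee and the participants have a correct picture of how long the supported positions are held. The planned analysis is not at stake.

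**Working it through.** **Inputs**

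- Stated exposure: 70 min (Section 9).
- Length of a condition: about 20 min, followed by a 3-min break (Section 6.1).
- Number of conditions: 7, all done by every participant in one visit (Sections 5.1.1 and 6.1).
- Conditions by position (Figure 1). The figure labels the standing row SS, where the text uses US. It is read here as unsupported standing, because the other two rows are high and low seating.

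**Step 1. Count conditions by position.** The two parts of Figure 1 differ on condition E. The letter list gives E the same label as G (low seating, low height). The grid instead has a high-seating, low-height cell that the list lacks.

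| Position | Grid | Letter list |
|---|---|---|
| Unsupported standing | 2 | 2 |
| High seating | 3 | 2 |
| Low seating | 2 | 3 |
| Supported (high + low) | 5 | 5 |

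The count of supported conditions is five either way.

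**Step 2. Try to reproduce 70 min.** Exposure = number of conditions × 20 min.

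- All supported: 5 × 20 = 100 min.
- High seating only: 3 × 20 = 60 min (grid) or 2 × 20 = 40 min (list).
- Low seating only: 2 × 20 = 40 min (grid) or 3 × 20 = 60 min (list).
- Unsupported standing: 2 × 20 = 40 min.

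Because 70 is not a multiple of 20, no set of whole 20-min conditions produces it.

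**Step 3. Ask whether the approximate 20 min closes the gap.** The condition length needed for a total of 70 min is 70 / k:

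- k = 5 (all supported): 14 min.
- k = 4: 17.5 min.
- k = 3 (one seating position): 23.3 min.

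For the five supported conditions, each would have to be 6 min, or 30%, shorter than stated. Rounding does not explain that.

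**Step 4. Cross-check the 20 min.** Section 6.2 gives about 80 s per work cycle. 20 × 60 / 80 = 15 cycles, or 5 at each of three working distances if these share the time equally (an assumption). At 14 min the result is 840 / 80 = 10.5 cycles, or 3.5 per distance. The 20 min is therefore consistent with the task description. This does not settle which passage is intended.

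**Step 5. Size of the gap, if semi-standing means the supported conditions.** 100 − 70 = 30 min, and 30 / 100 = 30%. Familiarization wear of 15 to 30 min would raise 100 to 115 or 130 min. Force-plate trials in supported positions would add more, but the length of most of them is not given.

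**The case against.** The strongest reply is that *semi-standing* may not mean all supported work. High seating could be what the authors had in mind, and on the grid that is about 60 min, not far from 70. Adding the four high-seating force-plate trials at an assumed 80 s each gives 60 + 4 × 80 / 60 = 65.3 min. Adding three breaks instead gives 60 + 3 × 3 = 69 min.

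Part of this stands. The term is undefined, so the 100-min comparator is a reading, and a high-seating reading cannot be ruled out. But neither sum is stated anywhere. The first needs 10 / 4 = 2.5 min per trial to reach 70, which the documents do not give. The second counts only three of the breaks and treats as exposure time that begins with walking. Both also need the grid rather than the letter list.

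A reader might also infer more than the documents support:

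- **That the exposure is understated by half, 70 against 7 × 20 = 140 min.** That total includes 2 × 20 = 40 min of unsupported standing, which is hard to call semi-standing.
- **That participants are told a shorter time than they will undergo.** Section 9 says they will be informed of the side-effects, not that the 70 min is quoted to them. The participant information is not available here.
- **That conditions were meant to last 10 min, since 7 × 10 = 70, so less data per condition will be collected.** Nothing in the plan documents such a length, and 10 min would give 600 / 80 = 7.5 cycles, or 2.5 per distance.

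Finally, the risks are worded qualitatively and no probability is calculated from the 70 min. That is correct, and it limits the severity.

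**Conclusion.** The point holds as a minor inconsistency. The 70 min in Section 9 has no stated derivation, uses an undefined term, and does not equal any whole number of conditions at the length given in Section 6.1.

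If semi-standing means the five supported conditions, the stated exposure is 30 min, or about 30%, below the scheduled 100 min. That size rests on this reading and on taking the approximate 20 min at face value. It does not depend on the conflict over condition E. If the term means high seating only, the mismatch is in the other direction: 60 min by the grid or 40 min by the letter list, before any trials.

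The documents do not show which passage is wrong. No endpoint, model, randomization scheme or sample size depends on the figure.

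**What to change.** 1. Define *semi-standing* in Section 9 using the position names of Section 5.1.1, stating whether it covers high seating, low seating or both.
2. Reconcile Section 9 with Section 6.1 and Figure 1. Derive the exposure from the scheduled conditions, broken down by position, and say whether breaks, force-plate trials and familiarization wear are counted. The investigators must state which passage reflects the intended schedule.
3. Make the grid and the letter list in Figure 1 agree on condition E, since the split by position depends on it.
4. If the participant information repeats the 70 min, align it with the reconciled figure.

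The cost is one definition, one figure and one label. The stated exposure may come out longer than it is now. The planned analysis is unchanged unless the investigators find that the condition length in Section 6.1 is the passage to amend.
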